5.5.2. Withdrawal Procedures

In the event that the decision is made to permanently discontinue the study treatment, the subject will be withdrawn, and the EOT visit should be conducted. Reasonable efforts should be made to have the subject return for all follow-up visits (see Section 6.4). The last date of the last dose of study treatment and the reason for subject withdrawal will be recorded in the eCRF.

If a subject is withdrawn from the study treatment:

- The study monitor or sponsor must be notified.
- The reason(s) for withdrawal from treatment must be documented in the subject's medical record and in the eCRF.
Note: The reason for withdrawal from treatment may be different than the reason for withdrawal from study. For example, subjects can discontinue treatment for disease progression or toxicity but remain in the study for safety follow-up.
- The EOT visit should be performed.
- The date of the EOT visit should be recorded in the eCRF and IRT.
- Subjects must be followed for safety until the time of the follow-up visit, or until study treatment-related toxicities resolve, return to baseline, or are deemed irreversible, or until the subject begins new anticancer therapy, whichever is longest.

If the subject discontinues study treatment and actively withdraws consent for collection of safety follow-up data, then no additional data collection should occur; however, **subjects will have the option of withdrawing consent for study treatment but continuing in the follow-up period of the study for safety assessments.**

5.6. Concomitant Medications

All concomitant medications and treatments must be recorded in the eCRF. Any prior medication received up to 28 days before the first dose of study treatment and 60 days after the last dose of study treatment, or until the subject begins a new anticancer therapy, whichever occurs first, will be recorded in the eCRF. Any addition, deletion, or change in the dose of these medications will also be recorded. Concomitant medications administered after 60 days after the last dose of study treatment should be recorded for SAEs as defined in Section 8. Concomitant treatments/procedures that are required to manage a subject's medical condition during the study will also be recorded in the eCRF.

5.6.1. Permitted Medications

All treatments that the investigator considers necessary for a subject's welfare may be administered at the discretion of the investigator in keeping with the community standards of medical care. All concomitant medications will be recorded on the eCRF, including all prescription, over-the-counter, herbal supplements, and IV medications and fluids. If changes occur during the study period, documentation of drug regimen, frequency, route, and date may also be included on the eCRF. *Note:* The use of bisphosphonates and denosumab are permitted in this study.

5.6.2. Restricted Medications

Systemic glucocorticoids for any purpose other than prophylaxis for contrast allergies for radiographic procedures, or to modulate symptoms or treat an AE of suspected immunologic etiology, are restricted and require medical monitor approval. The use of physiologic corticosteroid replacement therapy may be approved after consultation with the medical monitor.

Note: Inhaled and topical steroids are allowed. A short course of steroids (prednisone or equivalent) ≤ 10 mg/day may be permitted with medical monitor approval.

5.6.3. Prohibited Medications

Medications or vaccinations specifically prohibited in the exclusion criteria (see Section 3.2) are not allowed during the study. If there is a clinical indication for one of these medications or vaccinations specifically prohibited during the study, discontinuation from study treatment may be required. The investigator should discuss any questions regarding this with the medical monitor. The final decision on any supportive therapy or vaccination rests with the investigator and/or the subject's primary physician. However, the decision to continue the subject on study treatment requires the mutual agreement of the investigator, the sponsor, and the subject.

Subjects are prohibited from receiving the following therapies during the screening and treatment periods of this study:

- Any anticancer medications, including chemotherapy or biologic therapy other than study treatment.

- Any immunological-based treatment for any reason from screening through the safety follow-up visit is prohibited.

Note: Completed adjuvant therapy (eg, vaccines) with medical monitor approval, inhaled or topical steroids, systemic steroids at doses \leq 10 mg/day prednisone or equivalents, and immune suppressants are allowed for treatment for immune toxicities as described in Section 5.4.7 and [Appendix B](#), or as prophylaxis for contrast allergy for imaging procedures.

Note: Allergy shots may be permitted after consultation with the medical monitor.

- Investigational agents other than study treatment. Use of such medications from screening through the safety follow-up visit is prohibited.

- Concomitant radiation therapy.

Note: Radiation therapy to a symptomatic solitary lesion or to the brain may be considered on an exceptional case-by-case basis after consultation with the medical monitor. The subject must have clear measurable disease outside the radiated field. Administration of palliative radiation therapy will be considered clinical progression for the purposes of determining PFS.

- Live vaccines within 30 days before the first dose of study treatment and while participating in the study. Examples of live vaccines include, but are not limited to, the following: measles, mumps, rubella, chicken pox, yellow fever, rabies, *Bacillus Calmette–Guérin*, and typhoid (oral) vaccine. Seasonal influenza vaccines for injection are generally killed virus vaccines and are allowed. However, intranasal influenza vaccines are live attenuated vaccines and are not allowed.

Subjects who, in the assessment by the investigator, require the use of any of the aforementioned treatments for clinical management should be removed from the study. Subjects may receive other medications that the investigator deems to be medically necessary. The exclusion criteria describe other medications that are prohibited in this study. There are no prohibited therapies during the post-treatment follow-up period.

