5.5. Withdrawal of Subjects From Study Treatment

5.5.1. Withdrawal Criteria

A subject may choose to withdraw from the study treatment at any time or be withdrawn from the study treatment by the investigator or sponsor, if the subject is noncompliant with the study requirements. If a subject is withdrawn from study treatment, then every reasonable effort should be made to determine the reason for withdrawal, and this information should be recorded in the eCRF.

Subjects **must** be withdrawn from **study treatment** for the following reasons:

- The subject becomes pregnant.
- Consent is withdrawn. Subjects may choose to withdraw from the study at any time without penalty of jeopardizing their health care or loss of benefits to which the subject is otherwise entitled.
Note: Consent withdrawn means that the subject can no longer be followed and no additional data can be collected. Subjects may choose to discontinue study treatment and remain in the study to be followed for safety through the safety follow-up period.
- Further participation would be injurious to the subject's health or well-being, in the investigator's medical judgment.
- Unacceptable toxicity (see Section 5.4.9). Subjects with unacceptable toxicities must be withdrawn from study treatment but will continue in the follow-up phase of the study (see Section 6.4).
- The study is terminated by the sponsor.
- The study is terminated by the local health authority, IRB, or IEC.
- The subject has received 24 months of treatment with study drug.

A subject **may** be discontinued from **study treatment** as follows:

- Confirmed radiographic progression of disease per RECIST v1.1 (see Section 7.7.1). A subject may be granted an exception to continue on treatment with confirmed radiographic progression if clinically stable or clinically improved (see Section 7.7.1). **Note:** For unconfirmed progression, see Section 7.7.1.
- If, during the course of the study, a subject is found not to have met eligibility criteria (see Section 3), the medical monitor, in collaboration with the investigator, will determine whether the subject should be withdrawn from the study.
- If a subject is lost-to-follow-up or noncompliant with study procedures or study treatment in the investigator's opinion, the sponsor should be consulted for instruction on handling the subject.

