6.3. End of Treatment

When the subject permanently discontinues study treatment, the EOT visit should be conducted. If the EOT visit coincides with a regular study visit, the EOT evaluations will supersede those of that scheduled visit, and the data should be entered in the EOT visit in the eCRF. The subject should be encouraged to return for the safety follow-up visits.

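### Protocol 5.6.3 takes subjects who need a prohibited treatment off the study, while 4.4, 5.5.2, 6.3 and 6.4 keep subjects who stop treatment in safety follow-up, so AE capture depends on which section a site follows

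*Protocol*

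**What the plan says.** Protocol 5.6.3 lists therapies barred during screening and treatment: other anticancer medication, immunological-based treatment (with exceptions), other investigational agents, concomitant radiation (with case-by-case exceptions) and live vaccines. It then says that subjects who, in the investigator's assessment, "require the use of any of the aforementioned treatments for clinical management should be removed from the study".

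The first paragraph of 5.6.3 is softer. For medications or vaccinations barred by the exclusion criteria it says that "discontinuation from study treatment may be required", and it leaves room to stay on treatment: "the decision to continue the subject on study treatment requires the mutual agreement of the investigator, the sponsor, and the subject". The section closes with "There are no prohibited therapies during the post-treatment follow-up period", which presupposes that such a period exists.

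Elsewhere the protocol separates stopping treatment from leaving the study. Section 5.5.2 notes that "subjects can discontinue treatment for disease progression or toxicity but remain in the study for safety follow-up". Section 5.5.1 says "Subjects may choose to discontinue study treatment and remain in the study to be followed for safety through the safety follow-up period", and says that subjects with unacceptable toxicity "must be withdrawn from study treatment but will continue in the follow-up phase of the study". Section 4.4 moves anyone who discontinues treatment into the follow-up period. Section 6.3 adds: "The subject should be encouraged to return for the safety follow-up visits". Section 6.4 sets safety visits at 30 and 60 days after the last dose and AE monitoring for at least 60 days, or until new anticancer therapy if that comes first.

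**The concern.** One subject can fall under two instructions. A site that applies 5.5.2 and 6.4 performs the end-of-treatment visit, schedules both safety visits and keeps recording AEs. A site that applies the closing part of 5.6.3 literally may take the subject off study when the need for the therapy is recognised, with no follow-up specified.

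Frequency, duration and severity of AEs are the Phase 1 primary endpoint (2.2.1), and only Phase 1 will be analysed (section 9). Section 5.4.7 warns that immune-related AEs can arise months after the last dose, and 5.4.2 allows toxicity seen after the DLT window to lower the MTD. The SAE window in 8.3.2 ends at the earliest of the last study visit, 60 days after the last dose or new anticancer therapy, so early removal could shorten SAE reporting as well. SAP 6.2 tabulates treatment discontinuation and study withdrawal separately, so the disposition table also depends on the reading.

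**Working it through.** The plan gives no figure to reproduce. The check is a comparison of sections, followed by a bound on the follow-up at stake.

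| Protocol section | What happens to the subject |
|---|---|
| 5.6.3, opening | Treatment may have to stop; continuing is possible by agreement |
| 5.6.3, after the list | Leaves the study |
| 5.6.3, last sentence | Assumes a post-treatment follow-up period |
| 4.4 | Enters follow-up when treatment stops |
| 5.5.1 | Need for a prohibited therapy is not a listed withdrawal reason |
| 5.5.2 | End-of-treatment visit, then followed for safety |
| 6.3, 6.4 | Safety visits at 30 and 60 days; AEs for at least 60 days or to new anticancer therapy |
| 6.5 | Need for a prohibited therapy is not a way to complete the study |

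No section says that removal in 5.6.3 means removal from treatment only. The conflict is most direct with 5.5.2. Sections 5.5.1 and 6.3 contribute through their general rules and do not mention prohibited therapies.

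**Follow-up at stake per subject.** Count days from the last dose. Let *r* be the day the therapy is judged necessary and the subject is removed, and *s* the day a new anticancer therapy starts.

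- *New anticancer therapy.* Sections 6.4 and 8.1.2 stop AE collection at *s* under either reading. For *s* up to 60 the loss is *s* − *r*, which is short unless the start is delayed. The safety visit that 6.4 and 7.5 place before the new therapy is also skipped.
- *Listed treatment that is not anticancer therapy*, such as a live vaccine or immunological treatment outside the exceptions. The loss is 60 − *r*, at most about 60 days when *r* = 0.
- *Radiation outside the exceptions.* The documents do not say whether it counts as new anticancer therapy, so either case could apply.

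**Effect on reported incidence.** The full analysis set (9.1) keeps every dosed subject in the denominator, so lost follow-up can only remove subjects from the numerator. If all 52 enrolled subjects were dosed, one subject whose only event in a category goes unrecorded moves the pooled incidence by 1/52 = 1.9 percentage points, downward. The share is larger in the tables by treatment group and dose. The documents give no count of affected subjects, so no total can be calculated.

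**The case against.** The best defence is that the sentence is loosely worded. The synopsis times the end-of-treatment visit from withdrawal from study. Section 5.5.1, under reasons for stopping treatment, asks whether an ineligible subject should be withdrawn from the study. A subject removed from the study is necessarily off treatment, and 5.5.2 then calls for the end-of-treatment visit and safety follow-up. Sections 6.4 and 8.1.2 tie AE monitoring to the last dose without reference to study status. SAEs suspected to be drug-related are reportable even after 60 days (8.3.2). A site reading the whole protocol might therefore lose nothing.

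That defence makes the benign reading plausible but does not settle it. Because the protocol distinguishes the two kinds of withdrawal and the SAP reports them separately, a site may reasonably follow the literal words.

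A reader might also infer more than the text supports:

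- *That the wording must mean full removal.* The loose usage above shows otherwise.
- *That every progressing subject is caught.* The list applies mainly to the screening and treatment periods. Once treatment has stopped for progression, the last sentence of 5.6.3 lifts the prohibitions. For immunological treatment and investigational agents the list itself runs through the safety follow-up visit, which is a further inconsistency within the section.
- *That subjects treated for immune-related AEs are removed.* Section 5.6.3 exempts immune suppressants used for immune toxicity.
- *That PFS is generally affected.* SAP Table 7 censors at the last valid scan when new anticancer treatment starts, and 5.6.3 already counts palliative radiation as progression for PFS. At most, a death in the lost interval, before documented progression and before any new therapy, could be missed.
- *That AE incidence is understated by several points.* This needs the number of subjects affected and their event rate, and the documents give neither.

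**Conclusion.** The inconsistency is real, stands in the current text and is not resolved elsewhere. Its reach is limited. Follow-up is lost only if a site applies 5.6.3 literally and the subject would otherwise have attended, which 6.3 merely encourages. The loss is the need-to-start interval and one safety visit for new anticancer therapy, and up to about 60 days for other listed treatments. The number affected is unknown, and the direction of any effect on AE incidence is downward. Sample size, DLT rules and error rates are unchanged. It is worth correcting because it concerns the primary endpoint and the correction is small.

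**What to change.** Reconcile 5.6.3 with 5.5.2, 6.3 and 6.4. State that a subject who needs a listed therapy still has the end-of-treatment visit and the 30- and 60-day safety follow-up that those sections require, unless consent is withdrawn or new anticancer therapy starts as described in 6.4. Whether and when study treatment stops is for the sponsor to settle; the opening and closing parts of 5.6.3 need to agree on it. In the same edit, align the end of safety follow-up in 5.5.2, which takes the longest of several endpoints, with 6.4 and 8.1.2, which take the earliest.

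For subjects already taken off study under 5.6.3, add a listing with the reason, the date of last dose and the days of follow-up after it, placed beside the TEAE tables. If the listing is empty, that settles the matter for the report.

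The cost is a small wording change and one listing. The visits are already in the schedule of assessments (Table 12).

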6. STUDY ASSESSMENTS

All study assessments will be performed as indicated in the schedule of clinical assessments ([Table 12](#)), and all laboratory assessments will be performed as indicated in [Table 13](#). [Table 14](#) presents a summary of clinical laboratory analytes to be assessed. The order of assessments is suggested by the order of mention within the schedule. See Section 7 for instructions on each assessment. Further details of study procedures and assessments can be found in the study reference manual or applicable procedural documentation.

Table 12: Schedule of Clinical Assessments

Visit Day (Range)	Protocol Section	Screening	Treatment ^a					Post-Treatment ^b		
			Cycles 1 and 6		Cycles ≥ 10 Weeks	All Other Cycles	Every 8 Weeks	EOT	Safety Follow-Up Visit 1	Safety Follow-Up Visit 2
			Day 1	Day 8	Day 1	Day 1	Disease Status			
Evaluation/Window	Day -28 to -1			± 1 day	± 3 days	± 3 days	± 7 days	± 3 days	30 days (+ 7 days)	60 days (+ 7 days)
Administrative procedures										
Informed consent	7.1	X								
Inclusion/exclusion criteria	3.1, 3.2	X	X ^c							
Contact IRT	7.2	X	X		X	X		X		
Medical and cancer history	7.3.1, 7.3.2	X								
Prior/concomitant medications	7.4	X	X	X	X	X		X	X	X
Administer INCAGN01949	5.2.1.1		X ^d		X ^d	X ^d				
Administer nivolumab	5.2.2.1		X ^e		X ^e	X ^e				
Administer ipilimumab	5.2.2.2		X ^f		X ^f	X ^f				
Poststudy anticancer therapy status	7.5								X	X
Clinical procedures/assessments										
Comprehensive physical examination (including height)	7.6.2.1	X								
Targeted physical assessment	7.6.2.2		X	X ^g	X	X		X	X	X
Vital signs and weight	7.6.3	X	X	X ^g	X	X		X	X	X
ECOG performance status	7.8.1	X	X	X ^g		X				
Laboratory assessments	7.6.5	X	X	X	X	X		X	X	X
12-lead ECG ^h	7.6.4	X								
AE assessment	7.6.1	X	X	X ^g	X	X		X	X	X
Efficacy measurements										
Radiologic tumor assessments	7.7	X ⁱ					X ^j	X ^k		

^a Treatment cycles will be Q2W (14 days ± 3 days).

^b The safety follow-up visits should be conducted approximately 30 days and 60 days after the EOT visit (or after the last dose of study treatment if the EOT visit was not performed) or before the initiation of a new anticancer treatment, whichever comes first.

^c Assessment of inclusion/exclusion criteria is only required at Cycle 1 Day 1.

^d In Treatment Groups G and K, INCAGN01949 is only administered on Day 1 of Cycles 1 and 2.

^e In Treatment Groups C, E, G, H, K, and L, nivolumab administration begins at Cycle 3 Day 1.

^f For subjects enrolled into Treatment Group B (INCAGN01949 + ipilimumab) and Treatment Groups D and J (INCAGN01949 + nivolumab + ipilimumab), ipilimumab will be administered on Cycle 1 Day 1 and then Day 1 of every third cycle (Cycle 1, Cycle 4, Cycle 7, etc). In Treatment Groups E, K, and L, ipilimumab administration begins at Cycle 3 Day 1 and then continues on Day 1 of every third cycle. If higher doses of ipilimumab are tested (eg, 3 mg/kg every 3 weeks [21 days] for 4 doses), then ipilimumab will be administered every 3 weeks for a total of 4 doses. If the scheduled ipilimumab doses fall on days other than Day 1 of a cycle, the subjects will need to be present in clinic for the infusion, and any standard procedures required by the site should be performed.

^g Only required for Cycle 6 Day 8 if subject is experiencing AEs > Grade 2.

^h All 12-lead ECGs will be performed with the subject in a recumbent or semirecumbent position after 5 minutes of rest and should not be performed within 15 minutes after a blood collection.

ⁱ The initial tumor imaging will be performed within 28 days before the first dose of study treatment. Images of the chest, abdomen, and pelvis are required for all subjects. Scans performed as part of routine clinical management are acceptable for use as the screening scan if they are of diagnostic quality and performed within 28 days before the first dose of study treatment. The same imaging technique should be used for a subject throughout the study. Local reading (investigator assessment with site radiology reading) will be used to determine eligibility and for subject management.

^j On-study imaging will be performed at Week 8 and then every 8 weeks (\pm 7 days) for the first 12 months (until the Week 56 scan) and then every 12 weeks (\pm 7 days) thereafter. Imaging should follow calendar days starting with Day 1 of INCAGN01949 treatment and should NOT be adjusted for delays in cycle starts. If imaging shows disease progression, then another imaging assessment should be performed at a minimum of 4 weeks but no later than 6 weeks later to confirm progression per mRECIST.

^k If scan was obtained within 4 weeks before the date of treatment discontinuation, then a scan at treatment discontinuation (EOT) is not mandatory. For subjects who discontinue study therapy without confirmed disease progression, a radiologic evaluation should be repeated at the time of treatment discontinuation (ie, date of discontinuation \pm 4 week window).

Table 13: Schedule of Laboratory Assessments

Visit Day (Range)	Protocol Section	Timing of Assessment	Screening	Treatment								Post-Treatment			
				C1		C2	C4	C6		C7	Every 4th Cycle (C8, C12)	All Other Cycles	EOT	Safety Follow-Up Visit 1	Safety Follow-Up Visit 2
				D1	D8	D1	D1	D1	D8	D1	D1	D1			
Evaluation/Window		Day -28 to -1		± 1 day	± 3 days	± 3 days	± 3 days	30 days (+ 7 days)	60 days (+ 7 days)						
Local laboratory tests^a															
Comprehensive serum chemistries ^b	7.6.5	N/A	X ^c	X ^d	X	X	X	X		X	X	X	X	X	X
Hematology with differential	7.6.5	N/A	X ^c	X ^d	X	X	X	X		X	X	X	X	X	X
Coagulation panel ^e	7.6.5	N/A	X ^c												
Urinalysis	7.6.5	N/A	X ^c												
Endocrine function tests	7.6.5	N/A	X ^c				X				X		X	X	
Hepatitis B and C	7.6.5.2	N/A	X												
Serum pregnancy test (childbearing females only) ^f	7.6.5.1	N/A	X										X		
Urine pregnancy test (childbearing females only)	7.6.5.1	N/A													

^a All safety laboratory assessments will be performed locally.

^b If liver chemistry tests increase in grade from baseline or are ≥ Grade 3, then liver chemistry monitoring should increase to once per week until resolved to baseline or ≤ Grade 1. Liver chemistry does not need to be monitored once per week indefinitely for persistent low grade abnormalities. Appropriate liver chemistry monitoring intervals should be discussed with the medical monitor for these circumstances.

^c Screening laboratory tests must be performed within 7 days of Cycle 1 Day 1. If performed more than 7 days before Cycle 1 Day 1, then the tests must be repeated and eligibility confirmed before study treatment administration on Cycle 1 Day 1.

^d Only required to be performed at Cycle 1 Day 1 if the screening assessment was not performed within 7 days.

^e Subjects on anticoagulation treatment should have parameters monitored throughout the study as clinically indicated.

^f A serum pregnancy test will be required for all women of childbearing potential during screening and must be within 72 hours before the first dose of study treatment.

^g Urine pregnancy tests will be conducted as medically indicated or per country-specific requirements.

Table 14: Local Laboratory Tests: Required Analytes

Serum Chemistries	Hematology	Urinalysis	Hepatitis Screening	Coagulation
Albumin	Complete blood count, including:	Color and appearance	Hepatitis B surface antigen	PT
Alkaline phosphatase	
 • Hemoglobin • Hematocrit • Platelet count • Red blood cell count • White blood cell count 	pH and specific gravity	Hepatitis B core antibody	aPTT
ALT		Bilirubin	HBV-DNA	INR
AST		Glucose	HCV antibody	
Bicarbonate		Ketones	HCV-RNA	
Blood urea nitrogen		Leukocytes		
Calcium		Nitrite		
Chloride		Occult blood		
Creatinine		Protein		
Glucose				
Lactate dehydrogenase	Differential count, including:			
Phosphate	
 • Basophils • Eosinophils • Lymphocytes • Monocytes • Neutrophils 			
Potassium				
Sodium	Absolute values must be provided for:			
Total bilirubin				
Direct bilirubin (if total bilirubin is elevated above ULN)	White blood cell differential laboratory results:			
Total protein	
 • Lymphocytes • Neutrophils 			
Uric acid				
Amylase				
Lipase				

^a If considered standard by your region.

